**Investigator Interests:**

Does the principal investigator, or do any research personnel who are responsible for the design, conduct or reporting of this project or any of their family members (spouse or dependent child) have an incentive or interest, financial or otherwise, that may affect the protection of the human subjects involved in this project, the scientific objectivity of the research or its integrity? Note: The Principal Investigator (Project Director), upon consideration of the individual's role and degree of independence in carrying out the work, will determine who is responsible for the design, conduct, or reporting of the research.

See Disclosures and Management of Personal Interests in Human Research

<http://www.yale.edu/hrpp/policies/index.html#COI>

Yes      X No

Do you or does anyone on the research team who is determined by you to be responsible for the design, conduct or reporting of this research have any patent (sole right to make, use or sell an invention) or copyright (exclusive rights to an original work) interests related to this research protocol?

Yes      X No

If yes to either question above, list names of the investigator or responsible person:

*The Yale University Principal Investigator, all Yale University co-investigators, and all Yale University individuals who are responsible for the design, conduct or reporting of research must have a current financial disclosure form on file with the University's Conflict of Interest Office. Yale New Haven Hospital personnel who are listed as co-investigators on a protocol with a Yale University Principal Investigator must also have a current financial disclosure form on file with the University's Conflict of Interest Office. If this has not been done, the individual(s) should follow this link to the COI Office Website to complete the form: <http://www.yale.edu/coi/>*

NOTE: The requirement for maintaining a current disclosure form on file with the University's Conflict of Interest Office extends primarily to Yale University and Yale-New Haven Hospital personnel. **Whether or not they are required to maintain a disclosure form with the University's Conflict of Interest Office, all investigators and individuals deemed otherwise responsible by the PI who are listed on the protocol are required to disclose to the PI any interests that are specific to this protocol.**

## SECTION II: GENERAL INFORMATION

1. **Performing Organizations:** Identify the hospital, in-patient or outpatient facility, school or other agency that will serve as the location of the research. Choose all that apply:

**c. Additional Required Documents (check all that apply):**

- |  |                |
|--|----------------|
|  N/A  | Approval Date: |
|  *YCCI-Scientific and Safety Committee (YCCI-SSC)  | Approval Date: |
|  *Pediatric Protocol Review Committee (PPRC)   | Approval Date: |
|  *YCC Protocol Review Committee (YRC-PRC)  | Approval Date: |
|  *Dept. of Veterans Affairs, West Haven VA HSS   | Approval Date: |
|  *Radioactive Drug Research Committee (RDRC)   | Approval Date: |
|  YNHH-Radiation Safety Committee (YNHH-RSC)  | Approval Date: |
|  Magnetic Resonance Research Center PRC (MRRC-PRC)   | Approval Date: |
|  YSM/YNHH Cancer Data Repository (CaDR)  | Approval Date: |
|  Dept. of Lab Medicine request for services or specimens form  |                |
|  Imaging on YNHH Diagnostic Radiology equipment request form (YDRCTO request) found at http://radiology.yale.edu/research/ClinTrials.aspx |                |

*\*Approval from these committees is required before final HIC approval is granted. See instructions for documents required for initial submission and approval of the protocol. Allow sufficient time for these requests. Check with the oversight body for their time requirements.*

2. **Probable Duration of Project:** State the expected duration of the project, including all follow-up and data analysis activities. **7 years**

3. **Research Type/Phase: (Check all that apply)**

a. **Study Type**

- Single Center Study  
 Multi-Center Study

Does the Yale PI serve as the PI of the multi-site study? Yes  No

- Coordinating Center/Data Management  
 Other:

b. **Study Phase**  N/A

- Pilot
  Phase I
  Phase II
  Phase III
  Phase IV  
 Other (Specify)

4. **Area of Research: (Check all that apply)** Note that these are overlapping definitions and more than one category may apply to your research protocol. Definitions for the following can be found in the instructions section 4c:

- |  |   |
|--|---|
|  Clinical Research: Patient-Oriented                |  Clinical Research: Outcomes and Health Services |
|  Clinical Research: Epidemiologic and Behavioral               |  Interdisciplinary Research                                 |
|  Translational Research #1 ("Bench-to-Bedside")                |  Community-Based Research                                   |
|  Translational Research #2 ("Bedside-to-Community") |   |

5. Is this study a clinical trial? Yes  No

*NOTE the current ICMJE (International Committee of Medical Journal Editors) definition of a clinical trial: “any research study that prospectively assigns human participants or groups of humans to one or more health-related interventions to evaluate the effects on health outcomes.” Health-related interventions include any intervention used to modify a biomedical or health-related outcome (for example, drugs, surgical procedures, devices, behavioral treatments, dietary interventions, and process-of-care changes). Health outcomes include any biomedical or health-related measures obtained in patients or participants, including pharmacokinetic measures and adverse events”*

If yes, where is it registered?

Clinical Trials.gov registry

Other (Specify)

Registration of clinical trials **at their initiation** is required by the FDA, NIH and by the ICMJE.

*If this study is registered on [clinicaltrials.gov](http://clinicaltrials.gov), there is new language in the consent form and compound authorization that should be used.*

For more information on registering clinical trials, including whether your trial must be registered, see the YCCI webpage, <http://ycci.yale.edu/researchers/ors/registerstudy.aspx> or contact YCCI at [contact])

6. Does the Clinical Trials Agreement (CTA) require compliance with ICH GCP (E6)?  
Yes  No

7. Will this study have a billable service? *A billable service is defined as any service rendered to a study subject that, if he/she was not on a study, would normally generate a bill from either Yale-New Haven Hospital or Yale Medical Group to the patient or the patient’s insurer. The service may or may not be performed by the research staff on your study, but may be provided by professionals within either Yale-New Haven Hospital or Yale Medical Group (examples include x-rays, MRIs, CT scans, specimens sent to central labs, or specimens sent to pathology). Notes: 1. There is no distinction made whether the service is paid for by the subject or their insurance (Standard of Care) or by the study’s funding mechanism (Research Sponsored). 2. This generally includes new services or orders placed in EPIC for research subjects.*

Yes  No

If answered, “yes”, this study will need to be set up in OnCore, Yale’s clinical research management system, for Epic to appropriately route research related charges. Please contact [[contact]](mailto:[contact])

8.. Are there any procedures involved in this protocol that will be performed at YNHH or one of its affiliated entities? Yes \_\_\_ No X *If Yes, please answer questions a through c and note instructions below. If No, proceed to Section III.*

- a. Does your YNHH privilege delineation currently include the **specific procedure** that you will perform? N/A
- b. Will you be using any new equipment or equipment that you have not used in the past for this procedure? N/A
- c. Will a novel approach using existing equipment be applied? N/A

If you answered “no” to question 8a, or "yes" to question 8b or c, please contact the YNHH Department of Physician Services ([name]) for prior approval before commencing with your research protocol.

*Please note that if this protocol includes Yale-New Haven Hospital patients, including patients at the HRU, the Principal Investigator and any co-investigators who are physicians or mid-level practitioners (includes PAs, APRNs, psychologists and speech pathologists) who may have direct patient contact with patients on YNHH premises must have medical staff appointment and appropriate clinical privileges at YNHH. If you are uncertain whether the study personnel meet the criteria, please telephone the Physician Services Department at [contact]. **By signing this protocol as a PI, you attest that you and any co-investigator who may have patient contact has a medical staff appointment and appropriate clinical privileges at YNHH.***

**SECTION III: FUNDING, RESEARCH TEAM AND TRAINING**

1. **Funding Source:** Indicate all of the funding source(s) for this study. Check all boxes that apply. Provide information regarding the external funding source. This information should include identification of the agency/sponsor, the funding mechanism (grant or contract), and whether the award is pending or has been awarded. Provide the M/C# and Agency name (if grant-funded). If the funding source associated with a protocol is “pending” at the time of the protocol submission to the HIC (as is the case for most NIH submissions), the PI should note “Pending” in the appropriate section of the protocol application, provide the M/C# and Agency name (if grant-funded) and further note that University (departmental) funds support the research (until such time that an award is made).

PI	Title of Grant	Name of Funding Source	Funding	Funding Mechanism
[name]	Working with HIV clinics to adopt addiction treatments using Implementation Facilitation (WHAT IF?)	National Institute on Drug Abuse	 Federal  State  Non Profit  Industry  Other For Profit  Other	 Grant- R01 DA041067  Contract#  Contract Pending  Investigator/Department Initiated  Sponsor Initiated  Other, Specify:

IRB Review fees are charged for projects funded by Industry or Other For-Profit Sponsors. Provide the Name and Address of the Sponsor Representative to whom the invoice should be sent. *Note: the PI's home department will be billed if this information is not provided.*

**Send IRB Review Fee Invoice To:**

N/A

2. **Research Team:** List all members of the research team. Indicate under the affiliation column whether the investigators or study personnel are part of the Yale faculty or staff, or part of the faculty or staff from a collaborating institution, or are not formally affiliated with any institution. **ALL members of the research team MUST complete Human Subject Protection Training (HSPT) and Health Insurance Portability and Accountability Act (HIPAA) Training before they may be listed on the protocol. See NOTE below.**

## SECTION V: RESEARCH PLAN

1. **Statement of Purpose:** State the scientific aim(s) of the study, or the hypotheses to be tested.

The specific aims with respect to increasing uptake of effective counseling and medications for tobacco, alcohol and opioid use disorders (addiction treatments) in four HIV clinics are:

**Aim 1.** Among key stakeholders, to use quantitative and qualitative (mixed) methods to identify the site-specific evidence, context and facilitation-related barriers and facilitators to the integration of addiction treatments to help tailor an Implementation Facilitation for each clinic.

**Aim 2.** To evaluate the impact of Implementation Facilitation on:

2a: Organizational readiness to deliver addiction treatments

2b: Provider readiness to deliver addiction treatments

2c: Provision of addiction treatments

2d: Changes in organizational models of care used to deliver addiction treatments

**Aim 3.** To evaluate the impact of Implementation Facilitation on ART receipt, viral suppression, VACS Index, and retention in HIV care among patients eligible for addiction treatment.

2. **Background:** Describe the background information that led to the plan for this project. Provide references to support the expectation of obtaining useful scientific data.

**Why focus on tobacco, alcohol and opioid use disorders?** These disorders are prevalent in HIV clinics, often co-occur, and effective counseling and medication treatments exist.

### **HIV clinics rarely provide treatment for tobacco, alcohol and opioid use disorders**

While effective addiction treatments exist, their use in HIV clinics is limited for a number of reasons at the patient, provider and organizational level. These include deficiencies in key stakeholder motivation, knowledge, prioritization and lack of a systematic approach to screening and treatment.

### **Integrating addiction treatments into HIV clinics can improve substance use and HIV outcomes**

Although there is limited literature on integrated treatment of HIV and substance use disorders in HIV clinics, evidence supports this approach.

**Models for optimal integration of addiction treatment in HIV clinics may vary by organization and substance** The implementation of addiction treatment into HIV clinics can be achieved using a range of models. Using the concept of the medical home, different models, using the skills of a range of HIV clinic providers such as nurses, social workers, physicians, nurse practitioners (NP), physician assistants (PA), pharmacists, and psychologists can support the integration of addiction treatment in HIV clinics. The model that is optimally efficient and effective for each clinic may vary based on the substance, organizational, provider and patient-level factors. The significance of the Implementation Facilitation strategy (Defined below) we will evaluate is that it allows for the models to be developed based on a clinic level assessment of facilitators and barriers (formative evaluation) with input from relevant stakeholders, and provides flexibility such that models may be tailored depending on the substance being addressed, organizational factors, provider comfort, knowledge, skills and attitudes and patient input.

## **Implementation Science and the PARiHS framework can guide efforts to promote the uptake of addiction treatment in HIV Clinics**

The field of Implementation Science can promote health care organization change and is gaining traction in the fields of HIV and Addiction Medicine. Implementation Science, defined by the National Institute of Health as *the study of methods to promote the integration of research findings and evidence into healthcare policy and practice*, provides organized approaches to help integrate addiction treatment into HIV clinics. We will ground the development of our Implementation Facilitation in the Promoting Action on Research Implementation in Health Services (PARiHS) framework. Our proposed research is consistent with a Hybrid Type 3 effectiveness-implementation study which focuses on simultaneously evaluating the impact of an implementation on provider and patient outcomes.

## **Implementation Facilitation leads to practice change**

Defined as a “process of ‘helping individuals and teams to understand what they need to change and how they need to change it in order to apply evidence to practice,’” Implementation Facilitation is an effective intervention that includes a “deliberate process of interactive problem solving and support that occurs in the context of a recognized need for improvement and supportive interpersonal relationship.” (Table 2)

**Research Plan:** Summarize the study design and research procedures using non-technical language that can be readily understood by someone outside the discipline. **Be sure to distinguish between standard of care vs. research procedures when applicable, and include any flowcharts of visits specifying their individual times and lengths.** Describe the setting in which the research will take place.

The **Working with HIV clinics to adopt Addiction Treatments using Implementation Facilitation (WHAT IF?)** study will evaluate the impact of Implementation Facilitation on the adoption of addiction treatment services in four HIV clinics. We will use a stepped wedge design (See Table 4). The stepped wedge design is a variation on a cluster randomized clinical trial in which participating sites are randomly assigned a time at which the intervention (Implementation Facilitation) is begun. The primary comparison is of the change that occurs from the pre-implementation period to two post-implementation periods, the initial six months (evaluation) and the following six months (maintenance). This proposal will consist of three main components in each of four clinics: 1) **formative evaluation** with key stakeholders at each site to guide and refine the Implementation Facilitation, 2) **conduct of the Implementation Facilitation** and 3) an **evaluation of the impact** of the Implementation Facilitation on organization and provider-level readiness, provision of addiction treatments, and HIV outcomes.

## **Intervention Sites**

The sites are the Immunology Center at Miriam Hospital in Providence, RI, , Hartford Hospital’s HIV Clinic in Hartford, CT, Haelen Center at Yale-New Haven Hospital, SUNY Downstate Medical Center’ HIV clinic in Brooklyn, NY. All sites have conducted research using their electronic medical records. The diverse sites’ commonalities and differences will drive local modifications to the Implementation Facilitation and enrich its generalizability. Table 3 provides estimates, where known, of the current need for and provision of addiction treatments

at the four sites. Currently, approximately 15% of eligible patients are receiving addiction treatments.

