**Table 3. Site Descriptions, Current Need and Provision of Addiction Treatments**

Site	Miriam Immunology Center	Boston Medical Center	Hartford Hospital	Downstate
Number of HIV-infected receiving care	1600	1200	500	1200
Number with untreated Tobacco Use Disorder	400	300	200	425
Number receiving on-site medication for tobacco use disorder (bupropion, NRT, varenicline)	140	Unknown	75	110
Number receiving on-site counseling for tobacco use disorder	Unknown	Unknown	50	7
Number with untreated Unhealthy Alcohol Use	100	200	75	240
Number receiving on-site medication for unhealthy alcohol use (naltrexone, acamprosate, disulfiram)	0	16	0	0
Number receiving on-site counseling for unhealthy alcohol use	Unknown	16	0	100
Number with untreated Opioid Use Disorder	80	100	80	100
Number receiving on-site medication for opioid use disorder (buprenorphine, naltrexone)	32	50	0	4
Number receiving on-site counseling for opioid use disorder	32	50	0	7

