### **Evaluating the Effectiveness of the Implementation Facilitation (Aim 2 and Aim 3)**

#### Overview

We will use a stepped wedge design (Table 4) to evaluate the effect of the Implementation Facilitation on the outcomes. In a stepped wedge design, clinics are randomly assigned to time cohorts and then followed prospectively to determine their outcome status. Stepped wedge designs are increasingly used to promote the implementation of evidence-based practice and are appropriate for evaluating interventions where there is evidence that the intervention is likely to be beneficial and when practical considerations require sequential deployment of an intervention. We will have three phases of six-months each: 1) a pre-implementation control period, 2) a post-intervention evaluation period, and 3) a maintenance period. The proportion of eligible patients in each time period who receive at least one addiction treatment will be assessed and the effect of the intervention will be evaluated by comparing pre-implementation to evaluation and maintenance periods. This will allow us to assess the short and long-term (maintenance) impact of Implementation Facilitation.

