**Table 5. Summary of Study Assessments**

Assessment	Data Source	Baseline Control	6 months Evaluation	12 months Maintenance
Organizational Readiness to Change Assessment	Provider and Organizational representatives	X	X	X
Change Rulers for each medication and counseling intervention	Provider and Organizational representatives	X	X	X
Conduct of screening for each condition	Electronic Medical Record	X	X	X
Use of each medication and counseling intervention	Electronic Medical Record	X	X	X
Patient demographic information	Electronic Medical Record	X	X	X
Receipt of antiretroviral therapy	Electronic Medical Record	X	X	X
Tobacco, Alcohol and Opioid Use Disorders	Electronic Medical Record	X	X	X
Psychiatric Diagnoses	Electronic Medical Record	X	X	X
Clinic Visits	Electronic Medical Record	X	X	X
Laboratory values	Electronic Medical Record	X	X	X
Receipt of benzodiazepines	Electronic Medical Record			X
Receipt of COVID-19 screening and COVID-19 diagnosis	Electronic Medical Record			X

Adequacy of sample size

Based on prior work, we anticipate that Implementation Facilitation will increase the proportion of eligible patients provided addiction treatment by the clinics from a baseline of 15% of eligible patients (Table 3) to 26% during the evaluation phase and 33% during the maintenance phase. This reflects an 11% absolute increase (75% relative increase) during the evaluation phase and a 19% absolute increase (125% relative increase) during the maintenance phase. A parallel group design, unadjusted for clustering and repeated measures would require a sample size of 592 (296 in each the control and intervention arms) to detect the estimated effect size (15% control vs. 26% intervention; power 90% and Type I error (alpha) of 0.05). We used the formula of Woertman et al. to incorporate the effect of the stepped wedge design. It was assumed that each clinic would provide a minimum of 300 addiction treatment eligible patients (n). In addition, the following assumptions were used, intracluster correlation,  $\rho = 0.01$ , number of steps,  $k = 4$ , number of baseline measurements,  $b=1$ , number of measurements taken after each

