step,  $t=1$ . With the above assumptions, the derived  $DE_{sw} = 0.63$ , thus yielding an adjusted sample size of 375 across the 4 clinics. This yields a sample size for the initial evaluation phase of 94 patients per clinic who are eligible for addiction treatment (tobacco, alcohol or opioid use disorder). Three primary time points will be used, control (six months) evaluation (six months) and maintenance (six months). Given we will have adequate power to detect a difference of a 11% increase in the provision of addiction treatments in the evaluation phase, we will be adequately powered for the 19% increase anticipated during the maintenance phase and for the other quantitative analyses proposed in Aims 2 and 3. This sample size estimated above is based on a ‘cross-sectional’ design. Even if the population in the clinics/clusters is assumed to be a stable ‘cohort’, the power will likely be more than sufficient due to within-patient correlation.

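### The 15% control rate is drawn from a table that has the wrong fourth clinic, and it does not follow from that table for a medication-or-counseling outcome

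*Combined protocol and SAP*

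**What the plan says.** Under Intervention Sites the participating clinics are Miriam, Hartford, the "Haelen Center at Yale-New Haven Hospital" and SUNY Downstate. The same section introduces Table 3 as giving estimates for the four sites and states that at present "approximately 15% of eligible patients are receiving addiction treatments". The second column of Table 3 is "Boston Medical Center"; there is no Haelen column. For each substance the table gives the number untreated, the number on medication and the number receiving counseling. Several cells read Unknown.

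The outcome is defined in the Overview of the effectiveness evaluation: "The proportion of eligible patients in each time period who receive at least one addiction treatment will be assessed". The paragraph on provision of addiction treatments counts both prescriptions and counseling, the latter by CPT code.

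The sample size paragraph expects provision to rise "from a baseline of 15% of eligible patients (Table 3) to 26% during the evaluation phase and 33% during the maintenance phase". It describes the first step both as 11 points absolute and as 75% relative. From 15% versus 26%, 90% power and alpha 0.05 it derives 592 patients in a parallel design, a stepped wedge design effect of 0.63, 375 in total, and "94 patients per clinic who are eligible for addiction treatment". The design effect assumes at least 300 eligible patients per clinic.

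**The concern.** The control rate is the one input to the sample size that is presented as observed in the trial's own clinics. It sets the variance, and the 26% and 33% targets are built on it. Its cited source describes a different set of clinics, and the printed counts, pooled for the stated outcome, lie above 15%.

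At 15% the two descriptions of the effect nearly coincide: 75% of 15% is 11.25 points. At a baseline above 20% they separate, and the required size moves in opposite directions depending on which one is meant. What is at stake is whether the stated targets and the figure of 94 per clinic describe this trial.

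**Working it through.** **1. Reproduce the plan's figure.** Inputs from the sample size paragraph: p0 = 0.15, p1 = 0.26, two-sided alpha 0.05, power 90%, n = 300, rho = 0.01, k = 4, b = t = 1. The plan names neither the sidedness nor the variance form. The two-sided, unpooled, continuity-corrected form is used here because it reproduces the stated 296.

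- n0 = (1.960 + 1.2816)² × [p0(1 − p0) + p1(1 − p1)] / (p1 − p0)² = 10.507 × 0.3199 / 0.0121 = 277.8
- With continuity correction: (n0/4) × [1 + √(1 + 4/(n0 × 0.11))]² = 295.7 per arm (plan: 296, total 592)
- Design effect: [1 + 0.01(1200 + 300 − 1)] / [1 + 0.01(600 + 300 − 1)] × 3(0.99) / [2(4 − 1/4)] = (15.99/9.99) × 0.396 = 0.634
- 592 × 0.634 = 375; 375/4 = 94

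The plan's arithmetic is sound given 15%.

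**2. Rebuild the control rate from Table 3.** Rate = treated / (treated + untreated), summed over substances, with Unknown as zero. Untreated totals are 2,300 with Boston and 1,700 without. The larger-count rows take the bigger of medication or counseling in each site-by-substance cell (full overlap). The no-overlap rows add the two.

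| Definition | Four columns as printed | Miriam, Hartford, Downstate |
|---|---|---|
| Medication only | 427/2727 = 15.7% | 361/2061 = 17.5% |
| Either, larger count | 530/2830 = 18.7% | 464/2164 = 21.4% |
| Either, no overlap | 689/2989 = 23.05% | 557/2257 = 24.7% |

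On pooled counts only the medication-only figure comes close to 15%. With Boston included it also treats Boston's unknown tobacco medication as zero while keeping Boston's 300 untreated tobacco patients in the denominator.

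**3. Allow for the missing clinic.** Haelen's counts are not in the documents. As an assumption, take 300 to 600 eligible there with 5% to 30% treated. The four-site rate is then about 15% to 20% for medication only, and about 18% to 23% for either treatment (larger count).

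**4. Carry the rates through the same formula.** Power at 94 per clinic is taken as parallel-group power at 296 per arm, with the design effect held at 0.634. At 300 per clinic the equivalent is 1200/0.634/2 = 947 per arm.

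| Control rate | Per clinic for +11 points, 90% power | Power at 94, +11 points | Power at 94, ratio 26/15 kept | Power at 300, +11 points |
|---|---|---|---|---|
| 15% | 94 | 90% | 90% | >99.9% |
| 21.4% | 2 × 354.5 × 0.634 / 4 = 112 | 84% | 99% | >99.9% |
| 24.7% | 2 × 378.7 × 0.634 / 4 = 120 | 81% | >99% | >99.9% |

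A pooled-variance version with continuity correction gives 114 and 122 per clinic, and 83% and 81% power, so the choice of formula matters little.

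**The case against.** The strongest reply is that nothing in the conduct of the trial changes. The 94 is a computed requirement and not a planned cluster size. The plan assumes at least 300 eligible patients per clinic from the electronic record, and at that size power for 11 points is above 99% at every baseline considered. This stands. A reader might infer that the trial is underpowered, or that its 90% power claim fails; the documents do not support that.

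A reader might also infer that 26% is nearly the status quo. Holding 26% fixed gives about 23% power at 94 per clinic from a 21.4% baseline and about 5% from 24.7%. But 26% was set as an increase from 15%, so a corrected baseline would move the target too. Those figures set a new baseline against an old target and should not be used.

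It is tempting to say that Table 3 counts medications only, or that 15% can be reached only that way. Table 3 has counseling rows, and the protocol never says how 15% was obtained. An unweighted mean of the site-by-substance rates, using the larger count, gives 14.9% over all four columns and 15.4% without Boston. The medication-only origin is therefore one possibility and no more.

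Finally, the rebuilt rates are rough. Table 3 offers estimates where known, its cells count disorders while the outcome counts patients, and the no-overlap bound is extreme: it treats Miriam's 32 opioid medication and 32 opioid counseling patients as different people. All this widens the uncertainty around the rebuilt rates; it does not supply a derivation of 15%.

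**Conclusion.** The point holds as a fault in the basis of the sample size. Table 3, the cited source of the 15%, includes a clinic that is not a site and omits one that is. The 15% does not follow from its pooled counts for the stated outcome, which give 18.7% to 23% as printed and 21.4% to 24.7% for the three listed sites. The true four-site rate cannot be computed without Haelen.

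The effect on the calculation depends on what is held fixed. With 11 points absolute, the requirement rises from 94 to about 112 to 120 per clinic, or power at 94 is about 81% to 84%. With the relative increase, power at 94 rises to about 99%. At 300 per clinic the 11-point comparison keeps more than 99% power under the plan's own model.

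These figures assume that Unknown means zero, that disorder counts stand for patients, that the three listed sites stand in for four, and that the plan's intracluster correlation of 0.01 and design effect apply.

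**What to change.** - Replace the Boston column of Table 3 with the Haelen Center's counts.
- Recompute the control rate for receipt of medication or counseling at the four actual sites, per patient if the records allow. Show numerator, denominator and the handling of Unknown cells.
- State whether the assumed effect is the absolute or the relative increase.
- Restate the 26% and 33% targets from the new rate. Give the required size, or the power at 94 per clinic, over a baseline range such as 15% to 25%.

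The cost is one data request to the Haelen Center, a revised table and a rewritten sample size paragraph. If the absolute effect is kept, the stated requirement becomes somewhat less favourable. No additional patients are needed.
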